2.2.2. Part 2 Dose Expansion

Type	Primary Objectives:	Primary Endpoints:
Efficacy	
 To assess preliminary clinical efficacy at RP2D for PF-06863135 as monotherapy and in combination with lenalidomide, pomalidomide, or dexamethasone. 	
 ORR (as Part 1) DOR (as Part 1)
	Secondary Objectives:	Secondary Endpoints:
Safety	
 To further characterize the safety and tolerability of PF-06863135 as monotherapy and in combination with lenalidomide, pomalidomide, or dexamethasone. 	
 Adverse Events as characterized by type, frequency, severity (as graded by NCI CTCAE version 4.03), timing, seriousness, and relationship to PF-06863135 treatment as monotherapy and in combination with pomalidomide, lenalidomide, or dexamethasone. The severity of CRS will be assessed according to the grading described by Lee et al. (2014 and 2019,^{2,3}; Laboratory abnormalities as characterized by type, frequency, severity (as graded by NCI CTCAE version 4.03), and timing.
Efficacy	
 To further evaluate anti-myeloma efficacy of PF-06863135 as monotherapy and in combination with lenalidomide, pomalidomide, or dexamethasone. 	
 Time to event endpoints (as Part 1) Rate of patients with no MRD after treatment with PF-06863135 using IMWG MRD criteria⁴.
PK	
 Evaluate PK of PF-06863135 at RP2D as monotherapy and in combination with lenalidomide, pomalidomide, or dexamethasone. Additionally, to collect lenalidomide, pomalidomide, and dexamethasone concentration data when combined with PF-06863135. 	
 Concentrations of PF-06863135, lenalidomide, pomalidomide, and dexamethasone at selected time points.
Immunogenicity	
 To evaluate immunogenicity of PF-06863135 as monotherapy and in combination with lenalidomide, pomalidomide, or dexamethasone. 	
 Incidence and titers of anti-drug antibodies (ADA) and neutralizing antibodies (Nab) against PF-06863135.

Biomarker	
 To characterize the impact of PF-06863135 as monotherapy and in combination with lenalidomide, pomalidomide, or dexamethasone on systemic soluble immune factors. 	
 Pre- and post-dose quantification of soluble cytokines in serum.
	Tertiary/Exploratory Objectives:	Tertiary/Exploratory Endpoint):
Biomarker	
 Evaluate the effect of PF-06863135 as monotherapy and in combination with lenalidomide, pomalidomide, or dexamethasone on plasma cell, T and B cell compartments. 	
 BCMA expression on plasma cells in bone marrow, as assessed by multiparameter flow cytometry and immunohistochemistry; Pre- and post-dose levels of soluble BCMA; Enumeration of T, B, and NK subtypes in whole blood and bone marrow by flow cytometry analysis; T-cell immunophenotyping, including but not limited to proliferation and activation markers in whole blood and bone marrow by flow cytometry analysis; T-cell engagement, including but not limited to proliferation and activation markers in bone marrow by immunohistochemistry; The relative expression of RNA transcripts, including but not limited to, those associated with immune activation and immune regulation in bone marrow and peripheral blood; The abundance and diversity of T-cell clones in bone marrow and peripheral blood.
Biomarker	
 To collect banked biospecimens for exploratory research, unless prohibited by local regulations or ethics committee decision. 	
 Collection of banked biospecimens unless prohibited by local regulations or ethics committee decision.

3. INTERIM ANALYSES, FINAL ANALYSES AND UNBLINDING

There are no formal interim statistical analyses in this open-label, unblinded clinical trial. Treatment safety and effectiveness are to be monitored continuously.

If the following criteria listed below are met in any of the cohorts in Part 2 dose expansion, further enrollment into the cohort meeting the criteria will be placed on hold, and a decision to stop the cohort may be made following a review of all safety information:

- Number of patients with *Grade 5 treatment-related AE $\geq 10\%$, or*
- Number of patients with *Grade 4-5 treatment-related non-hematological AE $> 25\%$.*

Adverse event information collected during dose escalation of subjects treated at the same dose levels will be included in the evaluation.

4. HYPOTHESES AND DECISION RULES

4.1. Statistical Hypotheses

Of the dose-escalation phase of the study, a Bayesian procedure is implemented to determine the MTD.

4.2. Statistical Decision Rules

The initial Study Decision rules are described in the following table:

Table 1. Decision Rules

Number of Subjects Having DLT	n=2	n=3	n=4	n=5	n=6	n=7	n=8	n=9	n=10	n=11	n=12
0	E	E	E	E	E	E	E	E	E	E	E
1	S	S	S	E	E	E	E	E	E	E	E
2	U	D	D	S	S	S	S	S	S	S	E
3		U	U	U	D	S	S	S	S	S	S
4			U	U	U	U	D	S	S	S	S
5				U	U	U	U	U	U	D	S
6					U	U	U	U	U	U	U

D: De-escalate the dose; E: Escalate the dose; S: Stay at the dose; U: Unacceptable toxicity

Note: If one subject has a DLT event observed in a dose cohort with 2 subjects enrolled, additional subjects may be enrolled for dose escalation assessment. Any DLT observed accounts for decision rules.

Dose escalation will stop under any of the following conditions:

- The maximum sample size has been achieved;
- 6-12 subjects have been enrolled at a dose that is predicted to be the MTD;
- All doses explored appear to be overly toxic and the MTD cannot be determined.

5. ANALYSIS SETS

Analysis Set	Description	Applicable Analysis (for additional information refer to section 6)
Full Analysis Set (FAS)	all enrolled participants.	Primary endpoint, main analysis (section 6.1.1.1)
DLT Evaluatable Set	patients that have experienced a DLT in the DLT observation period or received all of their planned doses of PF-06863135 in the initial DLT observation period if Q2W dosing is being evaluated or at least all but one of their planned doses of PF-0686135 if Q1W dosing is being evaluated, provided a dose was not missed due to toxicity attributed to study drug. Safety information from any patients that do not meet DLT evaluable criteria could still be considered for overall dose escalation decisions although they would not factor into mTPI decision rules.	DLT (see section 8.2.1)
Safety Analysis Set	all subjects who receive at least 1 full or partial dose of study medication.	DLT (see section 8.2.1) Safety (see Section 8.2.3) Demography and Baseline characteristics
PK Concentration Analysis Set	PF-06863135 PK Concentration Analysis Set is defined as all subjects randomized and treated who have at least 1 measurable PF-06863135 concentration.	PK Analysis (see Section 8.2.5.)
PK Parameter Analysis Set	PF-06863135 PK parameter analysis population is defined as all enrolled subjects treated who have sufficient information to estimate at least 1 of the PF-06863135 PK parameters of interest.	PK Analysis (see Section 8.2.5.)
PD/Biomarker Analysis Set	all enrolled subjects with at least 1 of the PD/Biomarkers evaluated at pre- and/or post-dose.	PD/Biomarker Endpoints (see Section 8.2.5.4)
Immunogenicity Analysis Set	PF-06863135 Immunogenicity analysis set: The immunogenicity analysis set is defined as patients who receive at least 1 dose of study treatment and have at least 1 ADA sample collected.	Immunogenicity Analysis(see Section 8.2.5.5.)
mITT Analysis Set (for evaluation of efficacy)	all subjects who have received at least one dose of study treatment. If the FAS is same as the mITT, the analysis should be run on FAS.	Efficacy Analysis (see Section 8.2.3)
Response Evaluatable Set	all patients who have received at least one dose of the study treatment, and has at least one post baseline efficacy assessment.	Efficacy Analysis (see Section 8.2.3)

5.1. Treatment Misallocations

This is an unblinded MTD dose finding study. Subjects will be included in the cohort defined by their initial dose.

5.2. Protocol Deviations

Protocol deviations will be defined and this analysis plan to be updated before database lock.

5.2.1. Deviations Assessed Prior to Randomization

At Screening, the investigator will assess subjects against the inclusion and exclusion criteria as set out in Sections 4.1 and 4.2 of the protocol.

5.2.2. Deviations Assessed Post-randomization

A full list of protocol deviations for the study report will be compiled prior to database closure. Any significant deviation from the protocol will be reviewed prior to database closure and a decision taken regarding evaluation for each analysis population.

6. ENDPOINTS AND COVARIATES

Baseline is defined as the last planned visit measurement on or prior to the first dose of study medication administration; otherwise, the last available measurement on or prior to the first dose of study medication administration is to be adopted as Baseline. The start date is defined as the first day of dosing.

6.1. Efficacy Endpoints

In this First in Patient study anti-tumor activity is a secondary objective for Part 1 and the primary objective for Part 2. All responses are as per investigator reported responses.

Endpoints are as shown in Section 2.2.

- **Complete Response** includes confirmed stringent Complete Response (sCR) and Complete Response (CR). CR Rate (CRR) is defined as the percentage of subjects meeting criterion for CB relative to the mITT analysis set.
- **Clinical Benefit** (CB) includes confirmed response of sCR, CR (with and without MRD negativity), VGPR, PR, and MR. CB Rate (CBR) is defined as the percentage of subjects meeting criterion for CB relative to the mITT analysis set.
- The **OR Rate** (ORR) is defined as the percentage of subjects meeting criterion for OR relative to mITT analysis set.

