9.4. Efficacy Analysis

In this First in Patient study, anti-myeloma activity is a secondary objective in Part 1 dose escalation. Objective response rate (ORR) and duration of response (DOR) are primary objectives in Part 2 dose expansion. Other efficacy endpoints are secondary objectives in Part 2. The analysis population is defined in [Section 9.1](#) Analysis Sets.

Imaging studies, relevant laboratory assessments, and bone marrow pathology may be collected to support independent central review for efficacy endpoints.

PF-06863135

C1071001

Final Protocol Amendment 9, 28 March 2023

Disease response will be presented in the form of patient data listings that include, but are not limited to starting dose, disease response at each visit, and best overall response. In addition, progression date, death date, date of first response and last disease assessment date, and date of last contact will be listed.

Best overall response (BOR) will be assessed based on reported overall responses at different evaluation time points using IMWG response criteria (see [Appendix 2](#)).^{4,5}

- **Complete Response** will encompass confirmed stringent Complete Response (sCR) and Complete Response (CR).
- **Overall Response (OR)** will encompass confirmed sCR, CR, VGPR (very good partial response) and partial response (PR).
- **Clinical Benefit (CB)** will encompass confirmed sCR, CR, VGPR, PR and MR.

Progression -free survival (PFS) is the time from start date of study treatment to date of first documentation of progression, or death due to any cause. Progression is defined as the appearance of local, regional or distant disease of the same type after complete response or progression of pre-existing lesions. It does not include second primary malignancies of unrelated types.

Overall survival (OS) is the time from start date of study treatment to date of death due to any cause.

Duration of Complete Remission is defined for patients with confirmed complete response (sCR, CR) as the time from the first documentation of complete response to the first documentation of objective tumor progression or to death due to any cause, whichever occurs first.

Duration of Response (DOR) is defined for patients with confirmed objective response (as defined above in overall response) as the time from the first documentation of objective tumor response to the first documentation of objective tumor progression or to death due to any cause, whichever occurs first.

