2. INTRODUCTION

This document describes the planned statistical analyses for Protocol C1071001 latest amendment, dated 06 Jun 2021. This SAP is meant to supplement the study protocol. This SAP supersedes the statistical considerations identified in the protocol and, where considerations are substantially different, they will be identified as such. Any deviations from this analysis plan will be described in the clinical study report (CSR). Any post-hoc, or unplanned analyses performed that are not specified in this SAP will be clearly identified in the CSR. This plan is developed and finalized prior to database lock of the clinical database. This SAP is written with consideration of the recommendations outlined in the International Conference on Harmonisation (ICH) E9 Guideline (Guidance for Industry: Statistical Principles for Clinical Trials) and on the ICH E3 Guideline (Guidance for Industry: Structure and Content of Clinical Study Reports).

Interim data may be analyzed and reported in an interim CSR at any timepoint (including at the primary completion date [PCD]) before the final ORR collection are complete. The following CSRs will contain any updated data collected after the interim CSR cutoff date.

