Efficacy	
 To evaluate anti-myeloma activity of PF-06863135 as monotherapy and in combination with lenalidomide, pomalidomide, or dexamethasone. 	
 ORR defined using the International Working Group (IMWG) response criteria for multiple myeloma and is the percentage of participants with best overall confirmed BOR of sCR, CR, VGPR, or PR relative to the appropriate analysis set. Time to event endpoints as follows: 
 TTR defined as the time from date of first dose to the first documentation of objective treatment response (PR, VGPR, CR, or sCR, whichever is earlier in participants with BOR of PR, VGPR, CR or sCR). CRR defined as the proportion of subjects with confirmed stringent Complete Response (sCR) and Complete Response (CR). CBR defined as proportion of subjects with a BOR of sCR, CR (with or without MRD negativity) VGPR, PR, and MR. DOR, defined as the time from the first documentation of OR to the first documentation of objective PD of progression, clinical relapse or to death due to any cause, whichever occurs first. DoCR or sCR, defined as the time from the

		
first documentation of complete response to the first documentation of objective progression, clinical relapse or death due to any cause, whichever occurs first.
 
 • DOSD is defined for patients with stable disease as the time from the first documentation of objective stable disease to the first documentation of objective tumor progression or to death due to any cause, whichever occurs first. • PFS, defined as the time from date of first dose to date of first documentation of objective PD of progression, or death due to any cause (progression as defined by IMWG response criteria for PD). • OS, defined as the time from date of first dose to date of death due to any cause. Subjects are censored at the time of last follow-up. • Rate of patients with no MRD (by lab data) after treatment with PF-06863135 using IMWG MRD criteria

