8.2.2. Efficacy Analyses

No formal hypothesis testing will be performed on analysis of efficacy endpoints.

Efficacy analysis will be summarized by dose cohorts. Analysis of progression free survival and time to progression are defined as time from the date of first dose. Summaries of the n and % of subjects with PFS, and TTR and data listing by tumor type and dose will be generated. If applicable, the PFS may also be summarized using the Kaplan-Meier method at all or some of the following timepoints:

- OS at 6, 9, 12, 18, 24 months timepoints
- PFS, DOR, DoSD and DoCR at 3, 6, 9, 12, 18 months timepoints
- Reverse KM Follow-up probability is 3, 6, 9 months timepoints

The 95% confidence intervals will be generated. Confidence intervals for medians and quartiles will be based on the Brookmeyer-Crowley method. Confidence intervals for the estimated probability of an event at a particular time point will be generated using the Greenwood formula. Duration of response will be summarized with number of responders, number and percentage of event/censorship, mean, standard deviation, minimum, maximum and median of duration in unit of months. ORR and CBR will be summarized by number of subjects meeting respective criteria, percentage. The 95% confidence intervals will be generated for PFS, TTR, ORR, and CBR. Definitions of PFS, TTR, DoR, ORR, and CBR are outlined below.

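### SAP 6.1 gives the complete response rate the clinical-benefit numerator, and SAP 8.2.4 reverses the dates in the AE duration formula

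*SAP*

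**What the plan says.** **Complete response rate.** In SAP 6.1 the complete response bullet opens correctly: complete response "includes confirmed stringent Complete Response (sCR) and Complete Response (CR"). It then states: "CR Rate (CRR) is defined as the percentage of subjects meeting criterion for CB relative to the mITT analysis set". The next bullet defines clinical benefit (CB) as a confirmed sCR, CR, VGPR, PR or MR and continues: "CB Rate (CBR) is defined as the percentage of subjects meeting criterion for CB relative to the mITT analysis set".

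Elsewhere the definition is narrower. SAP 2.2.1 has "CRR defined as the proportion of subjects with confirmed stringent Complete Response (sCR) and Complete Response (CR"). Protocol 9.4 says that complete response "will encompass confirmed stringent Complete Response (sCR) and Complete Response (CR").

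In the analysis section, ORR and CBR have their own subsections (SAP 8.2.2.8 and 8.2.2.9) and CRR has none. The general sentence in SAP 8.2.2 also leaves CRR out: "ORR and CBR will be summarized by number of subjects meeting respective criteria, percentage".

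**AE duration.** SAP 8.2.4 names CRS and ICANS as the AEs of special interest. It gives the duration of an AE as the start date minus the stop date, plus 1. Presentation under that formula is optional, but the same section commits to summarising and listing ICANS duration, and to analysing time to CRS resolution.

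**The concern.** If 6.1 is programmed as it reads, every patient whose best response is VGPR, PR or MR counts as a complete responder, and CRR and CBR carry the same number. CRR is a named secondary endpoint in Parts 1 and 2. The SAP also claims precedence: "This SAP supersedes the statistical considerations identified in the protocol". A programmer who uses the correct numerator departs from 6.1, and SAP Section 2 requires deviations from the plan to be described in the CSR. The wrong result would be a plausible percentage, so nothing in the output itself would flag it.

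If 8.2.4 is programmed as it reads, durations become zero or negative for every event longer than one day, and longer events rank below shorter ones. CRS duration matters in this trial. CRS was the most common TEAE (87.8% of 41 patients, Protocol 1.2.3.1), and Protocol 3.4 bases the priming strategy on shorter CRS.

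**Working it through.** **1. CRR against CBR**

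Inputs: the CRR, CB and CBR definitions in SAP 6.1; the CRR definition in SAP 2.2.1; complete response in Protocol 9.4.

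- CRR as written in 6.1 = n(CB)/n(mITT) = (sCR + CR + VGPR + PR + MR)/n.
- CBR in 6.1 = n(CB)/n(mITT), the same expression. So CRR = CBR for any data.
- CRR under SAP 2.2.1 and Protocol 9.4 = (sCR + CR)/n.
- Overstatement = (VGPR + PR + MR)/n.

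The documents do not give the VGPR, PR and MR counts, so the overstatement cannot be computed. A lower bound on the literal CRR can be, because CB contains every objective response, so CBR ≥ ORR.

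- Pooled: Protocol 1.2.3.2 reports a confirmed ORR of 63.4% in 41 patients at the full dose (26/41 = 63.4%). The literal CRR there is at least 63.4%.
- By cohort: the SAP's level of summary is "Efficacy analysis will be summarized by dose cohorts". The preliminary ORRs in Protocol 3.4 give the floors below. They assume that those responses were confirmed, which Protocol 3.4 does not say.

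| SC dose (µg/kg) | Responders/n | Floor for literal CRR |
|---|---|---|
| 215 | 3/4 | 75.0% |
| 360 | 3/4 | 75.0% |
| 600 | 4/6 | 66.7% |
| 1000 | 5/6 | 83.3% |

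For illustration only, assume a cohort of 20 with 3 sCR, 3 CR, 4 VGPR, 2 PR, 1 MR, 4 SD and 3 PD:

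- As written: (3 + 3 + 4 + 2 + 1)/20 = 13/20 = 65%, equal to CBR.
- Under SAP 2.2.1: (3 + 3)/20 = 6/20 = 30%.
- Difference: (4 + 2 + 1)/20 = 7/20 = 35 percentage points.

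**2. AE duration**

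Input: the formula in SAP 8.2.4. For an event of d calendar days counted inclusively, stop − start = d − 1. Then:

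- Correct: stop − start + 1 = d.
- As written: start − stop + 1 = −(d − 1) + 1 = 2 − d.

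| True duration (days) | SAP 8.2.4 as written |
|---|---|
| 1 | 1 |
| 2 | 0 |
| 3 | −1 |
| 4 | −2 |
| 9 | −7 |
| 30 | −28 |

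The two expressions agree only at d = 1; a day-by-day check from 1 to 60 days found all 59 values from 2 to 60 wrong. A mean duration m would be reported as 2 − m. The 9-day and 4-day CRS events in Protocol 3.4 differ by 9 − 4 = +5 days, but by (−7) − (−2) = −5 under the formula.

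The SAP's other duration formulas subtract the earlier date from the later one: OS (8.2.2.2), DoR (8.2.2.6), DoCR (8.2.2.7), DoSD (8.2.2.10) and duration of treatment (8.2.2.12). So does the time-to-onset formula that follows in 8.2.4.

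**The case against.** The best reply is that both are slips whose intent is plain.

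- SAP 6.1 sends the reader to Section 2.2, where CRR is right. TTCR, DoCR and the MRD summary among complete responders all take complete response as CR or sCR. CB for CR is probably a copying error between adjacent bullets.
- The precedence sentence goes on to say that substantial differences from the protocol will be identified. None is identified for CRR, so no change was meant.
- SAP Section 5 already assigns the mITT set, with the response evaluable set, to efficacy analyses. CRR would not lack a denominator without the faulty sentence, which is only the one CRR-specific statement of it.
- The percentages above are floors on a hypothetical result, from cohorts of 4 to 6 patients or from a pooled group. They do not measure bias.
- Negative durations would be noticed at once, and the formula's own lead-in makes its use optional.
- ORR, DOR, DLT assessment, dose decisions, stopping rules and sample size use neither quantity, and the SAP's summaries are non-inferential.

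All of this stands as a limit on the consequences. It does not make either rule correct. Recoverable intent means that correct output depends on someone overriding the text. Likely detection applies to the durations but much less to CRR, and ICANS duration is a committed output.

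**Conclusion.** Both points hold. CRR as defined in SAP 6.1 is identical to CBR and contradicts the preceding sentence of its own bullet, SAP 2.2.1 and Protocol 9.4. The overstatement is exactly (VGPR + PR + MR)/n. Its size is not derivable, but a literal CRR could not be below 63.4% in the pooled 41 patients. The cohort floors also need the confirmation assumption, and the 20-patient split is an assumption throughout.

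The AE duration formula returns 2 − d and is wrong for every event longer than one day; this follows from the formula alone and needs no assumption.

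The effect is on reporting a secondary endpoint and the AEs of special interest. It does not reach the Part 2 primary endpoints or dose finding. These are corrections that should be made, not threats to the design.

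**What to change.** - **SAP 6.1:** in the CRR sentence, replace the CB criterion with confirmed sCR or CR. Keep the mITT denominator.
- **SAP 8.2.4:** define the duration of an AE as stop date minus start date plus 1.

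The cost is a few words of SAP text and a check of two programmed derivations. No new data are needed and no clinical rule changes. Both edits bring the text back to the sponsor's own usage elsewhere in the documents.
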